#### **4.0 REGISTRATION PROCEDURE**

Patients must meet all eligibility requirements and sign an informed consent form prior to study enrollment. All patients will be registered by the Radiation Oncology Research Coordinators at [name] prior to treatment. The Research Coordinators will verify eligibility, and completion of pretreatment evaluations.

#### **5.0 RADIATION THERAPY: 3-D Based Treatment Planning**

##### **5.1 Brachytherapy/Target Visualization**

Patients will undergo an interstitial implant, either utilizing a prone stereotactic method or a supine, ultrasound-guided or CT-guided technique, both under local anesthesia. Multiple catheters must be placed either free-hand or with the template system. Single balloon intracavitory catheter (MammoSite) is not permitted.

##### **5.2 Target Volume Definition**

Radioactive implants following lumpectomy are intended to deliver a tumoricidal dose to the target volume. The delineation of this target volume is essential for prescribing a dose and dose distribution capable of sterilizing occult tumor foci in the breast tissue surrounding the excision cavity. The target can be defined either by surgical clips visualized on stereotactic digital mammography, ultrasound, or CT visualization of the post-surgical seroma with subsequent Omnipaque nonionic contrast injection. The target volume will be defined as the volume encompassed by an irregularly-shaped surface 1.5-2 cm outside the excision cavity in all dimensions unless limited by skin or chest wall.

##### **5.3 Implant Geometry Design**

- Peripheral coverage is obtained positioning at least one catheter on each side 1 cm or more beyond the target volume. The other dimension of peripheral coverage is determined by the length of the active sources within each catheter.
- The catheters must be parallel to each other and as straight as possible.
- The rigid template will be used for the prone stereotactic method. The advantage of templates is precise geometrical source distribution, but there may be a problem with coverage of a curved, irregularly-shaped target volume. This can be overcome by the addition of free-hand catheters in areas of potential cold spots, thereby improving geometric volume coverage. This free-hand technique will be used with ultrasound or CT guidance for the supine method.

##### **5.4 3-D CT Based Treatment Planning**

CT based planning will be used for dosimetric evaluation. Simulator-based planning is not permitted.

##### **5.5 Dose Prescription**

*High dose-rate:* Patients will receive either a total dose of 34 Gy given BID at 3.4 Gy per fraction (10 fractions), or 32 Gy given BID at 4.0 Gy per fraction (8 fractions) to be delivered with a high dose-rate Ir-192 source as an outpatient. Each fraction will be separated by a minimum of 6 hours.

### **5.6 Dosimetric Characteristics**

- Dose optimization will be guided by dose homogeneity index (DHI) which is defined as  $DHI = (V_{100}-V_{150})/V_{100}$ , where  $V_{100}$  and  $V_{150}$  are the volumes covered by the 100% and 150% isodose lines, respectively. The DHI must be between 0.7-1.0.
- The dose must be prescribed to a depth of  $\geq 5$  mm from the skin surface.
- The following dosimetric parameters must be recorded on the dosimetry form: (1) target volume, (2) seroma volume, (3) percent target covered by chosen isodose line, (4) # of catheters, (5) volume of implant, and (6)  $V_{100}$  and  $V_{150}$ , (7) DHI, and (8) NTDmeans of heart, lung, and contralateral breast from DVH analysis.

### **5.7 Photography Documenting Implant Geometry**

At least one digital image is required - a close-up encompassing the treated breast only in a position which optimally exhibits the implant geometry, taking care to exclude the patient's face.

### **5.8 Toxicity Reporting (Serious Adverse Effects):**

University of Wisconsin Hospital and Clinics has created a data and safety monitoring plan, and a data and safety monitoring board to closely monitor the proposed study (Appendix). Modified RTOG toxicity scoring will be utilized (Appendix).

## **6.0 SYSTEMIC THERAPIES**

- No prior chemotherapy. Subsequent systemic therapy will be at the discretion of the medical oncologist.
- Chemotherapy regimens should be started no earlier than 2 weeks after the removal of the brachytherapy catheters.
- Tamoxifen or other hormonal agents should not be given during brachytherapy.

## **7.0 PATHOLOGY**

- All outside pathology slides should be reviewed at UW.
- Measurement of the resected breast specimen should be obtained in three dimensions and recorded if possible (gross or microscopic measurement is acceptable).
- If of adequate size, tumor should be harvested for estrogen and progesterone receptor determination. Immunohistochemical staining is an alternative.
- HER2/neu testing should be done in all patients if possible.
- Multiple blocks of the primary tumor and of breast tissue from the inked margins should be taken, the latter to confirm negative margins. Margins generally are **positive** if there is invasive or noninvasive tumor at the inked resection margin, **close but negative** if the tumor is within 2mm of the inked margin, and **negative** if the tumor is  $> 2$ mm from the inked margin. Extent of negative margin should be recorded as ( $\leq 2$ mm; 2-10mm;  $\geq 10$ mm) if possible.

- Pathology report must include DCIS or invasive, LVI, lymph node status, histological subtype, grade, and EIC if present.

## **8.0 PATIENT ASSESSMENTS**

### **8.1 Study Parameters**

Assessment	Pre Rx	During/After Brachytherapy	Post RX 4-6 weeks	Post RX 6 mos.	Post RX 1 year
H & P (Initial Eval Form)	X				
Chest x-ray	X				
Lab studies a	X				
H & P (Follow-up Form)			X	X	Xc
Disease status	X		X	X	Xc
Toxicity Assessment		X	X	X	Xc
Mammograms	Xd			X	Xe
Cosmesis, Pt (Form)	X			X	Xb
Cosmesis, MD (Form)	X			X	Xb
Photographs	X	X	X	X	Xc
Questionnaire (QOL)	X	X	X	X	Xb

- a. CBC, platelets, PTT, PT, BUN, creatinine, lytes
- b. Yearly thereafter upto 5 years.
- c. Clinical examination and disease status assessment at 6 month intervals for the first 5 years and yearly intervals thereafter. (Can be done via clinic visit notes from other physicians involved in patient's care or via telephone follow-up).
- d. pre and post lumpectomy (if applicable)
- e. Every 6 months for 3 years and then yearly for 5 years (for treated breast) and yearly for opposite breast

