## **2.2 Secondary Objectives**

- To determine if brachytherapy will have non-inferior toxicity to external beam radiotherapy (5%) at 3 years. Grade 3 or higher toxicity will be scored.
- To evaluate cosmesis at each follow-up by utilizing a cosmesis score based on established Harvard criteria.
- To assess patient satisfaction with breast brachytherapy by a questionnaire pre-brachytherapy, at completion, and post-brachytherapy.
- To perform a dosimetric comparison with an external beam plan for each patient. The following parameters will be evaluated: skin dose, target coverage, dose homogeneity index, and NTDmeans from dose volume histograms for each individual patient for heart, lung, and contralateral breast.
- To assess the ability to interpret mammography after interstitial brachytherapy.
- To evaluate Disease-free, Mastectomy-free, and Overall Survival.

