### **10.1.2 Toxicity Assessment**

Patient will be seen on a daily basis by treating physician while receiving radiation therapy and during each follow-up visit. Toxicities resulting from brachytherapy will be collected and graded according to the Modified RTOG Toxicity Criteria (appendix). Any toxicities grade 3 or higher will be promptly reported to DSMB and IRB.

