## Appendix III: Follow-up Form

 If this is a revised or corrected form, indicate by checking box.		INSTRUCTIONS: Submit this form at the appropriate follow-up interval and whenever there is a change in the patient's status. Use -1 for unknown or not applicable unless otherwise specified in code table. Enter dates in mm-dd-yyyy.
PATIENT INITIALS: _____ STUDY ID #: _____ DATE OF EVALUATION ____-____-_____		CURRENT TUMOR STATUS
 # MONTHS SINCE BRACHYTHERAPY PROCEDURE		 NO EVIDENCE OF DISEASE
 PATIENT QUALITY OF LIFE FORMED COMPLETED?		 IPSILATERAL BREAST TUMOR RECURRENCE
 PATIENT COSMESIS FORM COMPLETED?		 LOCAL (infield) - within the prescription isodose volume
1 EXCELLENT 2 GOOD 3 FAIR 4 POOR		 PERIPHERAL - between the prescription isodose volume and a volume 2 cm outside of the prescription isodose volume.
 PHYSICIAN COSMESIS FORM COMPLETED? (Initials: _____)		 NON-CONTIGUOUS/EXTRA-FIELD - beyond the peripheral volume described above.
 RTOG TOXICITY SCORE: SKIN		 OTHER SITES OF CANCER RECURRENCE
GRADE 0 None GRADE 1 Slight atrophy; Pigmentation change; Some hair loss GRADE 2 Patch atrophy; Moderate telangiectasia; Total hair loss GRADE 3 Marked atrophy; Gross telangiectasia GRADE 4 Ulceration		 NODAL (Specify location) _____
 RTOG TOXICITY SCORE: SUBCUTANEOUS TISSUE		 CONTRALATERAL BREAST _____
GRADE 0 None GRADE 1 Slight induration (fibrosis) and loss of subcutaneous fat GRADE 2 Moderate fibrosis but asymptomatic; <10% linear reduction; Slight field contracture		 DISTANT METS (Specify location) _____
GRADE 3 Severe induration and loss of subcutaneous tissue; >10% linear measurement; Field contracture		 NEW PRIMARY LESION (Specify location) _____
GRADE 4 Necrosis		 MAMMOGRAM SINCE LAST VISIT
		1 No 2 Yes * *If yes, date of study _____-_____-
		 SUSPICIOUS FINDINGS ON MAMMOGRAM
		0 Not applicable/no mammogram 1 Negative mammogram 2 Microcalcifications only 3 Mass density only 4 Both, mass and microcalcifications 5 Other, Specify _____

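### Late RTOG grades may be recorded by telephone or from other physicians' notes although grade 3 needs examination, so the 3-year grade 3+ toxicity rate is at risk of being under-counted

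*Combined protocol and SAP*

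**What the plan says.** The first objective listed in Section 2.2 is "To determine if brachytherapy will have non-inferior toxicity to external beam radiotherapy (5%) at 3 years", and the event is fixed by the next sentence: "Grade 3 or higher toxicity will be scored".

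In the Section 8.1 table, the row "Toxicity Assessment" is marked with footnote c in the 1-year column. That footnote sets the schedule as "Clinical examination and disease status assessment at 6 month intervals for the first 5 years and yearly intervals thereafter" and then adds in brackets: "Can be done via clinic visit notes from other physicians involved in patient's care or via telephone follow-up". Section 9.1 repeats the bracketed permission against the Follow-up Form itself, under a heading that begins at 4-6 weeks.

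The Follow-up Form in Appendix III carries a late skin score and an item headed "RTOG TOXICITY SCORE: SUBCUTANEOUS TISSUE". For the latter the third level reads "GRADE 3 Severe induration and loss of subcutaneous tissue; >10% linear measurement; Field contracture". Grade 3 skin on the same form, and in Appendix IV, is marked atrophy or gross telangiectasia. The form offers -1 for unknown.

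Section 10.1.2 describes a different arrangement: "Patient will be seen on a daily basis by treating physician while receiving radiation therapy and during each follow-up visit". Section 10.2 reports the toxicity rate with an exact 95% confidence interval and includes all registered patients. It gives no toxicity margin, no decision rule and no rule for patients without a grade.

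**The concern.** The line between grade 2 and grade 3 depends on physical signs: the degree of atrophy, telangiectasia or induration, and whether contracture exceeds 10% on linear measurement. A telephone call cannot supply a palpation or a measurement, and nothing in the plan requires another physician's note to record either. A grade 3 sign that is present but not looked for goes unrecorded, and that error lowers the rate, towards the conclusion the objective hopes to reach.

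At stake is how the 3-year rate and its interval will be read against 5%. Section 1.0 also names women living far from a radiation centre among those for whom the conventional course is prohibitive. It is reasonable to expect, though the plan does not say, that such patients would use the remote option most.

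**Working it through.** **Plan's own figure.** There is none to reproduce. Section 10.1.1 gives power for local failure only; no power, margin or sample size is stated for toxicity.

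**Inputs from the documents.** Reference rate 5% at 3 years (Section 2.2); about 300 patients, all registered patients analysed, exact 95% interval (Section 10.2).

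**Assumptions.** The documents give none of the following.
- True 3-year grade 3+ rate: 8%, chosen because 24/300 has an exact 95% interval of 5.2% to 11.7%, wholly above 5%. It is the smallest such count; 23/300 gives 4.9% to 11.3%.
- f, the share of patients whose toxicity is scored only remotely.
- s, the probability that remote scoring records a grade 3+ event that is present.
- Events missed remotely stay in the denominator as non-events.

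**Formula.** Recorded rate = true rate × (1 − f + f × s). The last column is the exact binomial probability of recording 15 or fewer events in 300, that is 5% or less.

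| f | s | Calculation | Recorded rate | P(15 or fewer of 300) |
|---|---|---|---|---|
| 0 | n/a | 0.08 × 1 | 8.0% | 2.9% |
| 25% | 0.9 | 0.08 × (0.75 + 0.225) | 7.8% | 3.8% |
| 40% | 0.5 | 0.08 × (0.60 + 0.20) | 6.4% | 19% |
| 40% | 0 | 0.08 × 0.60 | 4.8% | 63% |
| 75% | 0.25 | 0.08 × (0.25 + 0.1875) | 3.5% | 93.5% |

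In the fourth row the expected count is 300 × 0.048 = 14.4. An observed 14/300 (4.7%) has an exact interval of 2.6% to 7.7%, so a true excess over 5% would no longer show.

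**The passages side by side.** Section 8.1 footnote c and Section 9.1 allow a contact without a visit and let the form holding the grades be completed from it. Section 10.1.2 has the treating physician see the patient at follow-up visits and ties toxicity grading to that. The Photographs row also carries footnote c, although a photograph cannot be taken by telephone, which suggests that the footnote was attached to more rows than its bracket suits.

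**The case against.** The strongest reply is that the remote route is optional and that the plan already schedules a physician's assessment at year 3. The Physician Cosmesis Form is due yearly to 5 years under footnote b, which has no remote option, and it codes telangiectasia, skin atrophy, fibrosis and dimpling. Section 8.5 adds yearly photographs examined for visible complications. This stands in part: some grade 3 signs would come to light that way. But the cosmesis form codes signs by how visible they are, not by RTOG grade or linear measurement, so it does not supply the endpoint.

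Second, footnote c's text names clinical examination and disease status, not toxicity, and a telephone contact need not be a visit in the sense of Section 10.1.2. That softens the conflict within Section 8.1. It does not help with Section 9.1, where the permission applies to the form that carries the grades.

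Third, grade 4 ulceration or necrosis could plausibly reach the study through a note or a call, so zero remote sensitivity is a worst case. This stands, and is why sensitivity is varied above.

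A reader might go further and infer three things that the documents do not support:
- That the 3-year rate is biased. How much the remote route will be used is not stated, and the effect may be negligible.
- That ungraded patients count as event-free. Section 10.2 includes all registered patients but is silent on missing grades, and -1 is available.
- That a non-inferiority test would be tipped. Section 10.2 specifies no toxicity test or margin; non-inferiority is only the wording of the objective.

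**Conclusion.** The point holds as a risk of under-ascertainment arising from a stated permission. The plan lets late RTOG grades be recorded without examination, while grade 3 is defined by findings that need one. The likely direction is downwards. The magnitude cannot be fixed from the documents: with a true rate of 8%, the assumed combinations span almost no loss to a loss of more than half the events. The upper part of that range depends on heavy remote use, low remote sensitivity and undetected events being treated as non-events, none of which the plan states. The matter concerns a descriptive secondary endpoint and leaves the primary analysis untouched. It is still worth settling, because the rate will be read against 5% and the correction is cheap.

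**What to change.** 1. Reconcile Section 8.1 (footnote c) and Section 9.1 with Section 10.1.2 by limiting the telephone and outside-notes option to disease status and survival.
2. Record the RTOG skin and subcutaneous scores by examination at the yearly visits where the Physician Cosmesis Form is already due under footnote b, including year 3.
3. On the Follow-up Form, require -1, not grade 0, whenever no examination took place.
4. In Section 10.2, report the 3-year grade 3+ rate with its exact interval over all registered patients, together with the number ungraded. Give the rate among examined patients as a sensitivity analysis only: patients who attend may differ from those who do not, so it should not replace the all-registered rate.
5. Remove the remote option from Photographs but keep the Section 8.5 schedule. Moving that row to footnote b would end photographs at 5 years, whereas Section 8.5 sets no end.

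**Cost.** Changes to protocol and form wording, with no added scheduled visit. Some 6-monthly toxicity entries become unknown, and the examined-only denominator shrinks by however many patients miss the yearly visit. If remote follow-up proves common, that loss will not be small, which is a further reason to report the number ungraded.

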### **8.2 Response Criteria - Treatment failure**

- The definition of a treatment failure is: histologic evidence of recurrent carcinoma, either invasive or non-invasive (except LCIS) in the ipsilateral breast at 5 years.
- Ipsilateral breast recurrences will be considered **local (infield)** if they occur within the prescription isodose volume, **peripheral** if between the prescription isodose volume and a volume 2 cm outside of the prescription isodose volume. Ipsilateral recurrences will be considered **non-contiguous or extrafield** if they are beyond the peripheral volume described above.
- Ipsilateral axillary, infraclavicular, internal mammary, or supraclavicular recurrence or distant metastases will not be considered a treatment failure unless accompanied by ipsilateral breast recurrence.

### **8.3 Toxicity Criteria**

- Patient will be seen on a daily basis by treating physician while receiving radiation therapy. Toxicities resulting from brachytherapy will be collected and graded according to the Modified RTOG criteria (Appendix IV). **Any toxicities grade 3 or higher will be promptly reported to DSMB and IRB as specified in the appendix.**

### **8.4 Definitions of Levels of Cosmetic Outcome:**

- Patients will be grouped according to chemotherapy or hormonal therapy. Cosmesis will be graded by the patient and the radiation oncologist pre-RT, 6

and 12 months after completion of therapy and at yearly intervals thereafter. Cosmesis will also be evaluated from the photographs submitted to investigators at required intervals. The following established cosmesis scoring system will be used:

- Excellent - When compared to the untreated breast, there is minimal or no difference in the size, shape or texture of the treated breast. There may be mild thickening or scar tissue within the breast or skin, but not enough to change the appearance.
- Good - There is mild asymmetry in the size or shape of the treated breast as compared to the normal breast. The thickening or scar tissue within the breast causes only a mild change in the shape.
- Fair - There is obvious difference in the size and shape of the treated breast. This change involves 1/4 or less of the breast.
- Poor - There is marked change in the appearance of the treated breast involving more than 1/4 of the breast tissue.

### **8.5 Photographs**

- Routine photographs must be taken of the post-surgical breast prior to catheter placement. At least one photograph of the breast with catheters in place, prior to loading the radioactive sources, is required. Photographs should also be taken at prior to implantation, 4-6 weeks, 6 months, 12 months post-implant, and yearly thereafter. Images will be evaluated for any visible complication, degradation, or improvement of cosmesis or local/regional treatment failure. Digital images will be used. Post surgical (*pre-catheter*) and all follow-up photographs should always follow the guidelines specified in the next section. Photographs will be kept with the patient's medical record.
- The first photograph should be a closeup encompassing only the treated breast at a 45° oblique with arms elevated over the head. The second photograph should be a straight frontal view of both breasts taken in either a standing or seated position with the patient's hands symmetrically placed on her hips, taking care to exclude her face and framing or focusing on both the treated and untreated breast to allow optimal comparison of the breasts for symmetry. .

## **9.0 DATA COLLECTION**

### **9.1 Summary**

#### **Prior to brachytherapy**

- Eligibility Checklist
- Initial Evaluation Form (Appendix III)
- Patient QOL form (Appendix III)
- Cosmesis Forms (Appendix III)

#### **At completion of brachytherapy**

- Patient QOL form (Appendix III)
- Treatment Toxicity Form
- Radiotherapy Treatment/Dosimetry Form (Appendix III)

#### **At 4-6 wks, 6 mo., and 12 months after implant; q 6 months up to 5 years, then annually. Also at progression/relapse and at death**

- Follow-up Form (Appendix III) -- Can be done via clinic visit notes from other physicians involved in patient's care or via telephone follow-up

#### **At 6 mo. and 12 months after the completion of therapy, then yearly up to 5 years**

- Cosmesis Forms
  - *Patient* (Appendix)

- *Radiation Oncologist* (Appendix III)
- Patient QOL form (Appendix III)

## **10.0 STATISTICAL CONSIDERATIONS**

### **10.1 Study Endpoints**

#### **10.1.1 Ipsilateral breast recurrences**

This is a one-arm equivalence trial comparing the local failure rate in 300 patients receiving brachytherapy to the historical mean event rate of 6% (see Table below) among patients given external beam radiation. The null hypothesis thus is that brachytherapy is worse than external beam radiation; the alternative hypothesis is that the two regimens are clinically equivalent, meaning that brachytherapy is not significantly worse than external beam. Symbolically

$$H_0: \text{Pr}(\text{Local Failure, brachy.}) > \text{Pr}(\text{Local Failure, EB}) + \Delta$$

$$H_A: \text{Pr}(\text{Local Failure, brachy.}) \leq \text{Pr}(\text{Local Failure, EB}) + \Delta,$$

where "Pr()" denotes the probability of its argument and  $\Delta$  is the margin of clinical equivalence. That is, we consider two regimens whose event probabilities differ by less than  $\Delta$  to be equivalent. For this study we take  $\Delta$  to be 5%.

The analysis will be conducted by calculating an exact 95% confidence interval for the probability of local failure in the brachytherapy group and noting whether it includes 11% (obtained as  $\text{Pr}(\text{Local Failure, EB}) + \Delta = 6\% + 5\%$ ). If it does then we will not reject the null hypothesis and equivalence cannot be concluded. If the confidence interval for the probability of local failure given brachytherapy falls entirely below 11% then we conclude that brachytherapy is clinically equivalent (or possibly superior) to external beam radiation as a treatment for these patients. If, among 300 patients, there are 23 local failures (7.7%) then the exact 95% confidence interval for the true failure rate will be (5.2%, 11.2%). If there are 22 failures (7.3%) then the confidence interval will be (5.0%, 10.8%). Therefore we will reject the null hypothesis and conclude equivalence if we observe 22 or fewer local failures.

Power here is the probability that we will reject the null hypothesis and conclude equivalence given that it truly holds. If the two regimens rates are identical, such that  $\text{Pr}(\text{Local Failure, brachy.}) = \text{Pr}(\text{Local Failure, EB}) = 6\%$ , then the power with 300 patients is 86%. If the brachytherapy rate is inferior to external beam by 2%, so that  $\text{Pr}(\text{Local Failure, brachy.}) = 8\%$  and  $\text{Pr}(\text{Local Failure, EB}) = 6\%$  (which is still within our definition of clinical equivalence) then power drops to 39%. However if the brachytherapy rate is superior to external beam by 2% so that  $\text{Pr}(\text{Local Failure, brachy.}) = 4\%$  and  $\text{Pr}(\text{Local Failure, EB}) = 6\%$  then the power is 99.8%. Therefore if the local failure is 6% or less in the brachytherapy group then this study is well-powered to conclude equivalence within a margin of 5%.

Study	# Patients	5-year LF Rate (%)	Weighted LF rate
French	88	4.5	396
NSABP B-06	628	5	3140
NCI	121	2	242
Danish	430	5	2150
EORTC	456	11	5016
Milan	352	3	1056
Total/Mean	2075	5.08	5.78%

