### **10.1.7 Disease-Free Survival and Mastectomy-Free Survival**

All disease recurrences and surgical interventions will be recorded. In disease-free survival (DFS), any tumor recurrence or death will be considered a failure. In mastectomy-free survival (MFS), the failures will be mastectomy and death. Ipsilateral breast recurrence rate (subdivided by in-field, peripheral and extra-field locations) ipsilateral nodal recurrence rate and distant metastasis rate will be calculated.

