### **10.2 Study Design**

The sample size will be approximately 300 patients. The toxicity rate will be summarized along with exact 95% confidence intervals. DFS, MFS and OS

results will be summarized using Kaplan-Meier curves with the usual Greenwood estimates of standard errors. Summary statistics will be given for cosmesis, quality of life, dosimetric, and mammography interpretation measures. All analyses will be conducted on an intent-to-treat basis; that is, all registered patients will be included in the analyses.

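### The primary 5-year test has no rule for patients whose 5-year status is unknown, and the two decision rules in 10.1.1 part company once a few are lost

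*Combined protocol and SAP*

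**What the plan says.** Section 8.2 defines treatment failure as "histologic evidence of recurrent carcinoma, either invasive or non-invasive (except LCIS) in the ipsilateral breast at 5 years". Section 10.1.1 tests this rate against a limit of 11% (6% historical plus a 5-point margin) and gives two decision rules. The first is an interval rule: conclude equivalence if the exact 95% interval lies wholly below 11%. The second is a count, worked out from examples that begin "If, among 300 patients, there are 23 local failures (7.7%) then the exact 95% confidence interval" and ending: "Therefore we will reject the null hypothesis and conclude equivalence if we observe 22 or fewer local failures". On power, for a true rate of 6%, it says "then the power with 300 patients is 86" per cent.

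Section 10.2 states: "All analyses will be conducted on an intent-to-treat basis; that is, all registered patients will be included in the analyses". It gives a time-to-event method only for DFS, MFS and OS, whose "results will be summarized using Kaplan-Meier curves with the usual Greenwood estimates of standard errors". The sample size is described as approximately 300, with no allowance for loss.

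Follow-up is planned carefully. Section 8.1, footnote c, asks for "Clinical examination and disease status assessment at 6 month intervals for the first 5 years and yearly intervals thereafter" and accepts outside clinic notes or telephone contact. Section 9.1 asks for the Follow-up Form at relapse and at death. On deaths, section 10.1.7 is explicit for a different endpoint: "In disease-free survival (DFS), any tumor recurrence or death will be considered a failure". Neither 8.2 nor 10.1.1 mentions death for the primary endpoint.

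**The concern.** A rate at 5 years is being tested as a simple proportion. That works if every patient's status at 5 years is known. If some patients are lost earlier, the analyst has to keep them as non-failures, drop them or censor them, and the plan does not say which.

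The choice affects the result. A patient who is not observed cannot add to the observed failures. If that patient stays in the 300, the failure rate is pulled down, towards the conclusion the trial hopes to reach. If the patient is dropped, the denominator shrinks and the stated power no longer applies. This is the trial's only confirmatory test, so the choice should be fixed before outcomes are known.

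**Working it through.** **Inputs.** From 10.1.1: n = 300, limit 11%, cut-off 22, true rates of 6% and 8%. The documents give no loss rate; every loss figure below is an assumption, shown over 0-20%.

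**The plan's own figures.** P(X ≤ 22 | 300, p) is 86.2% at p = 0.06, 38.5% at 0.08 and 99.75% at 0.04. The plan states 86%, 39% and 99.8%, so these reproduce, provided all 300 have known status. At p = 0.11 the same probability, the one-sided error, is 2.2%. Clopper-Pearson upper limits are 10.89% for 22/300 and 11.28% for 23/300, which confirms the cut-off. (The printed intervals differ slightly from Clopper-Pearson; the cut-off does not change.)

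**Where the two rules diverge.** For 22/297 the Clopper-Pearson upper limit is 11.0003%. With three patients set aside as unknown, 22 failures passes the count rule and fails the interval rule. For 22/270 the interval is 5.2% to 12.1%.

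**Count rule applied to all registered patients.** Take constant hazards, with h = -ln(1-p)/5 for failure and d = -ln(1-L)/5 for loss of a share L. The probability of a recorded failure is

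q = h/(h+d) × (1 - exp(-5(h+d))).

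For p = 0.11 and L = 0.10: h = 0.02331 and d = 0.02107. Then exp(-5(h+d)) = 0.89 × 0.90 = 0.801, so q = 0.5252 × 0.199 = 0.1045, and P(X ≤ 22 | 300, 0.1045) = 4.2%.

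**Lost patients excluded, exact interval on the rest.** Two conventions are possible.
- Keep failures seen before loss and drop patients lost without failure. This raises the analysed rate. At p = 0.06 and L = 0.10, q = 0.0570 and the failure-free completers are 0.94 × 0.90 = 0.846, so the rate is 0.0570/(0.0570 + 0.846) = 6.3%.
- Assume the 6% rate holds among patients with known status, averaging over how many there are.

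The first gives the lower figure in each range below, the second the higher. Error at 11% stays at or below 2.4% in both.

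**Cumulative incidence with loss censored.** These figures come from simulation with a complementary log-log limit, independent loss, and 0%, 5% or 10% deaths.

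| Assumed loss | Count rule: error at 11% | Count rule: chance of equivalence at 6% | Lost excluded: power at 6% | Cumulative incidence: power at 6% |
|---|---|---|---|---|
| 0% | 2.2% | 86% | 86% | 86% |
| 2% | 2.5% | 87% | not computed | 83-84% |
| 5% | 3.1% | 89% | 80-83% | 83-84% |
| 10% | 4.2% | 91% | 74-80% | 82% |
| 20% | 7.9% | 94% | 59-75% | 79-80% |

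Cumulative-incidence error at 11% is 1.8-2.2% throughout. Plain Greenwood-type limits in the same settings give 3.4-4.4%.

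**Sensitivity to the kind of loss (count rule).** At 10% loss, error is 6.9% if all loss falls in year 1 and 2.5% if all falls in year 5. If lost patients fail at twice the hazard of the others, error is 3.9%, 6.5% and 14.3% at 5%, 10% and 20% loss. Censoring reduces these to 2.5%, 3.1% and 4.4% but does not remove the problem.

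**The case against.** The strongest reply is that the interval rule is the analysis and 22 is only its illustration at 300. Section 10.1.1 presents the interval first, and 10.2 says only approximately 300, so the cut-off has to move with the number analysed. On that view, excluding patients with unknown status does not inflate error. This stands: a reader might infer that the plan scores lost patients as non-failures, or that its error rate is inflated, and the documents say neither. That is one reading of the count rule combined with the all-registered principle. Including everyone registered could equally mean censoring. But the plan does not say that the interval rule governs or whom it covers, and excluding lost patients would sit uneasily with 10.2.

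A second reply is that follow-up is good and the harm modest. Six-monthly checks, outside notes and telephone contact do make heavy early loss less likely, and under late, independent loss the effect is small. These measures reduce loss; they are not an analysis rule.

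A third is that a single sentence on handling, keeping the exact interval, would close the gap. It would, and that is the minimum. Dropping lost patients, however, costs more power at 10% and 20% loss than the censored analysis on either convention at 20%, and on the less favourable one at 10%.

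A reader might also infer that deaths are mishandled. The failure definition in 8.2 requires histologic recurrence, which implies that a recurrence-free death is a non-failure. The plan leaves this implicit; it does not contradict itself.

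**Conclusion.** The gap is real: no section says how unknown 5-year status enters the primary test, and the stated 86% power holds only with complete 5-year status. Under the count rule with steady, independent loss, error at a true 11% stays within 2.5% up to about 2% loss (6 of 300). It then rises to 3.1%, 4.2% and 7.9% at 5%, 10% and 20% loss. It is larger with early or informative loss and about 2.5% at 10% loss if all loss is late. Under the alternative of excluding lost patients, the cost is power, not error. All of this rests on assumed loss rates and patterns and, for the count rule, on one of several possible readings. The point should be fixed, but it does not undermine the design, the margin or the cut-off for complete follow-up.

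**What to change.** Amend 10.1.1 as follows.

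1. Estimate the 5-year cumulative incidence of ipsilateral breast failure, as defined in 8.2, in all registered patients once all have 5 years of potential follow-up. Censor lost patients at their last disease assessment and treat recurrence-free death as a competing event.
2. Conclude non-inferiority if the upper two-sided 95% limit is below 11%, using a complementary log-log limit or another method with comparable coverage, not plain Greenwood limits.
3. State that this interval rule governs, and keep 22 of 300 only as the illustration for complete follow-up.
4. Add a tipping-point analysis giving the number of lost patients who would have to have failed to reverse the conclusion. In terms of the 22-of-300 illustration, 18 recorded failures need 5 more to reach 23, 20 need 3, and 22 need 1. This is needed because censoring does not fully cure informative loss.
5. Restate power at 6% as about 86% with no loss, 83-84% at 2-5%, 82% at 10% and 79-80% at 20%.

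The cost is SAP wording plus explicit recurrence and death dates on the Follow-up Form in Appendix III. That form already carries the evaluation date and months since brachytherapy, and is submitted at any change of status. Stated power drops by about 2-3 points at 2-5% loss, 4 at 10% and 7 at 20%. No extra visits or patients are needed.
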